## 4. RATIONALE

Our project aims to build on the work from the PERMIT studies to develop an *improved care* pathway for renal care in people living with heart failure. The care pathway will include an algorithm that will predict the risk of renal injury and disease progression based on previous renal function measurements. In addition, the algorithm will be used to guide optimal renal test frequency in individual people with heart failure. This will address the need for evidence-based guidelines on the frequency of renal testing function tailored for this specific cohort. Importantly, recommendations on renal testing frequency will be linked with evidence-based, consensus guidelines on appropriate interventions in cases with renal function decline, created with input from a panel of cardiologists, nephrologists and primary care practitioners, and our research team (including PPIE representatives).

These guidelines will be developed by the clinical experts panel the RENAL HF project. Potential interventions include adjustment of dose and type of medication and advice on fluid intake. These are all currently used to manage heart failure but without evidence-based guidance. This guidance is sorely needed due to the wide range of potential interventions: diuretic doses might be titrated up or down or discontinued temporarily; doses of ACEIs, ARBs, aldosterone antagonists or newer cardioprotective agents might be adjusted, commenced, or discontinued; important but non-pharmacological interventions might include increasing or decreasing 24-hour fluid restriction, increasing or decreasing recommended dietary potassium or salt intake.

Research to inform the development of an algorithm-guided care pathway has the potential to promote patient safety, enhance patient outcomes, and optimise available resources. This work will

provide better access to decision support for clinicians. Using AI and predictive techniques will enable a care pathway to improve patient outcomes aligning with current NHS priorities (12, 28). We estimate that 27,500 people with heart failure are admitted to the hospital due to renal impairment caused by medication per year in England (5). The median hospital stay for heart failure patients is nine days (29), and recovery after hospitalisation is typically slow, with frequent readmissions. The annual cost of AKI-related inpatient care in England (2011) was estimated at £1.02 billion, just over 1% of the NHS budget. Therefore, even a small reduction in admission rate would significantly save overall costs(30).

We shall focus on heart failure, a condition increasing in prevalence and most common in older adults with multimorbidity. Our multi-disciplinary team will turn data into information, creating a patient and practitioner-informed intervention. The knowledge we create will lead to a step-change in clinical practice. Our care pathway may increase the frequency of renal function monitoring for some patients. Conversely, monitoring could occur at a lower frequency for those at low risk of renal injury, reducing the burden to both the individual and the healthcare systems and contributing to optimal disease management. If a modest 5% decrease in hospital admissions could be achieved in this patient population, we estimate this would correspond to 1,375 admissions avoided per year across England. Although our intervention focuses on primary care, this will also benefit secondary care clinicians through shared care guidelines, improving the overall cross-speciality coordination of renal function assessment in people living with heart failure. Taken together, this will improve patient outcomes and satisfaction and reduce hospital admissions, aligning with the NHS Long Term Plan (28) goal of reducing the morbidity associated with cardiovascular disease.

## 5. RESEARCH AIMS

#### 5.1 Programme aims

This NIHR Programme Grant for Applied Research-RENAL-HF comprises five highly interconnected work packages (Figure 1), which aim to extend and refine our model to underpin an evidence-based system for generating guidelines for (i) personalised renal function monitoring and (ii) optimal interventions if renal function is declining.

Our aims for the full programme are shown below; WP 2 (Stages 1-5) objective 2 is considered in this protocol.

- Use advanced analytic methods and electronic health record data held by CPRD to advance
  the work from the PERMIT to refine the algorithm's accuracy that predicts the change in
  renal function in patients with heart failure. This work will involve the comparison of 2
  different methodologies, linear regression and machine learning (WP1) linear regression and
  machine learning in WP1
- 2. Co-create with patients, primary care practitioners and specialists the care pathway for implementing personalised renal function monitoring and optimal interventions if renal function is declining in primary care (WP2).
- 3. Assess the clinical effectiveness of our algorithm-guided clinical pathway, compared with the current standard-of-care, in a cluster randomised controlled trial (RCT) embedded within CPRD (WP3).
- 4. Perform health economic analyses to determine the cost-effectiveness of our algorithm-guided clinical pathway, which comprises personalised renal function monitoring and appropriate interventions (WP4).

5. Ensure that the patient voice is integrated throughout our studies, our findings and the subsequent guidance for people living with heart failure (WP5).

## **5.2 Work Package 2 Objectives and Outcomes**

By the end of the work described in this protocol we will refine the prototype training materials designed to enable primary care staff to preserve renal function in patient with heart failure, considering the views of key stakeholders including primary care staff and patients. During WP2 Stage 6 the care pathway (including renal function monitoring tool, user interface, alert system guidelines, and training materials) will be tested through a feasibility study before testing its utility in a trial during WP3. We anticipate that Stage 6 will be submitted as an early component of Work Package 3. By the end of WP2 we will have created an intervention, specified according to TIDieR guidelines(31), designed to change primary care practice and maximise future uptake and engagement of the new renal care pathway.

Study Stage	Objective	Outcomes
Stage 1a: Survey	To understand current practice	Refined early logic model to inform stage 2
Stage 1b: Interview	To identify barriers and facilitators to optimising the treatment of patients with heart failure while preserving renal function	Improved knowledge base to increase uptake of the future care pathway
Stage 2:	To work closely with critical stakeholders WP1 team and the expert clinical panel to develop prototype training material to ensure optimal design and uptake of the RENAL-HF care pathway ( which we anticipate will include personalised renal function monitoring, thresholds for intervention and clinical guidelines	Co-created prototype training materials for optimal implementation of the evidence based system
Stage 3	To consider the elements that will support optimal implementation of the evidence-based system in relation to the APEASE criteria	Intervention content and options for implementation for selected elements of the pathway
Stage 4	To develop online training materials that will support optimal implementation of the evidence-based system	Online training materials to support the care pathway
Stage 5	Beta testing	Refined prototype training material for the primary care teams
***Stage 6 (included for context only)	Evaluation work to ensure acceptability of the pathway for practitioners and patients Refine the prototype training material for the primary care teams	Co-created an intervention, which will be specified according to TIDieR guidelines(31)

#### 6. STUDY DESIGN

RENAL-HF Care pathway co-design (WP2 Stages 1-5) (months 1 - 24)

#### 6.1 Overview

The design of the RENAL-HF programme is informed by the MRC Framework and related guidance for developing and evaluating complex interventions (32-35). In addition to designing components of the intervention, attention will be given to understanding how and under what circumstance the intervention will bring about change and any potential barriers and enablers when implementing the care pathway. In addition, we will consider a broader range of questions relating to the context in which the intervention will be developed, implemented, and evaluated. To ensure practitioner

(particularly primary care) and patient acceptability of this new care pathway, we will integrate coproduction research methods (36, 37) involving the expertise of key stakeholder groups (including patients, primary care practitioners, specialists, and other key informants). Co-production research methods will ensure researchers, clinicians, and the public will work together throughout the research process, sharing responsibility from the start to the end of the project (38). This work will be informed by frameworks relevant to technology-based intervention development and implementation science, including the behaviour change wheel (39) and the non-adoption, abandonment, scale-up, spread, sustainability (NASSS) Framework(40, 41) and Toolkit (42) to support the design and implementation of the pathway in primary care practices.

#### 6.2 Methods

Within WP2, we will adopt a mixed methodology involving six iterative stages necessary to inform the development of a renal care pathway for people living with heart failure. To optimise recruitment during the uncertainty of the ongoing pandemic and the success of remote data collection in previous projects, we have included the option of remote data collection (video or telephone) in addition to face-to-face interviews.

## **6.3 Stage 1: Understanding current practice**

We will examine current practice through surveys and interviews with primary care practitioners involved in delivering the intervention to inform the optimal design and implementation process. The results from this stage will be used to refine the logic model (Appendix 3), illustrating how our intervention will enable primary care staff to take steps to preserve renal function in patients.

## 6.3.1 Stage 1a) Healthcare Professional Survey

We will conduct a survey of healthcare professionals in England, including GPs, pharmacists, and nurses (n=115 GPs, n=115 Pharmacists and n=370 Nurses), to establish patient and practitioner views on the current standard of care and to identify barriers and facilitators to optimising the treatment of patients with heart failure while preserving renal function. The survey is being codeveloped by our research team and public advisors and will be delivered through YouGov https://yougov.co.uk/, who have access to a representative healthcare workforce sample. The survey will first be piloted with clinical colleagues and then within YouGov with 50 members of their panel of healthcare professionals. Final refinements will be made, and then the survey will be delivered.

YouGov will be responsible for the recruitment of the required sample, secure data collection and sending the data to the research team for quantitative data analysis. Free text data will be analysed thematically using inductive thematic coding with mapping onto the theoretical domains framework (43). We will work closely with the University approved Client Engagement Manager for YouGov on the design, implementation, and analysis of this practitioner survey.

## 6.3.2 Stage 1b) Qualitative interviews

Two PDRAs, experienced in qualitative research methods, will conduct brief focused qualitative interviews with GPs, nurses and pharmacists recruited from Liverpool and Manchester primary care practices to generate options for intervention functions. We anticipate interviewing 17 participants per group; however, this number will be reduced if saturation is reached earlier. Early data collection

has indicated the importance of including the views of some Heart Failure Specialist Nurses (HFSNs) in addition to primary care-based nurses during Stage 1b

Informed by the behaviour change wheel (39), we shall use the capabilities, opportunities and motivations model of behaviour change(39) to structure the interviews and understand the drivers of optimising the treatment of patients with heart failure while preserving renal function. The topic guide is being co-developed by our research team and public advisors and will be piloted with clinical colleagues, following which final refinements will be made before data collection. According to individual preference, interviews will take place in person or remotely via video conferencing or telephone. Interviews will be audio-recorded, transcribed, checked and pseudo-anonymised before analysis. Data will be analysed using inductive thematic coding followed by mapping onto the theoretical domains framework (43).

## 6.4 Stage 2: Co-designing the care pathway-

#### 6.4.1 Evidence synthesis

The research team will synthesise the material generated in WP1 and the outputs from WP2 Stage 1 during a series of meetings to generate possible elements of the care pathway. These proposals will be rated during stakeholder workshops.

We anticipate that the evidence-based system developed by WP1, and the clinical expert panel will comprise three key outputs.

- 1 Personalised renal function monitoring schedules
- 2 Trigger points (thresholds) for intervention
- 3 Clinical guidelines to prevent renal decline.

The clinical expert panel comprised of cardiologists, nephrologists, clinical pharmacologists, and GPs will identify the best algorithm and clinical parameters for the key outputs. WP2 will generate intervention components that will enable the optimal design and uptake of this evidence-based system.

## 6.4.2 Stakeholder consensus workshops

We will use the RAND/UCLA Appropriateness Method (RAM) (44) involving diverse groups (including patients, specialists, primary care practitioners and other key informants) to ensure the views of key stakeholders are included in the design of the intervention. Typically, RAM involves only a single group of experts (e.g., nephrologists), but as the complexity of health care delivery increases, it is beneficial to adapt the RAM and similar methods of defining standardised quality care to include diverse healthcare professionals (45). Furthermore, there is a growing need to have patients, families, and caregivers in healthcare decision-making (24, 25). Therefore, our workshop design will comprise five stakeholder groups, including (patients, pharmacists, nurses, GPs, and key informants) each containing 9 participants.

Each group will engage in three rounds, rating the proposals created from the synthesis of WP1 and Stage 1 of WP2. The rounds will require: (i) independent individual ratings of appropriateness, (ii) moderated group ratings of appropriateness, and (iii) independent individual ratings of necessity.

We will set *a priori* criteria, informed by the RAND/UCLA Appropriateness Method (46) for group consensus, and undertake anonymised electronic voting, recording if and when consensus is reached. Consistent with the RAND/UCLA approach, the criteria for agreement for a 9-member panel will be a median of >7 on a 9-point Likert scale and no more than two members rating outside the 3-point region containing the median (i.e., 7–9 on a 9-point Likert scale). We anticipate that the workshop will comprise five parallel groups. The PPIE group will inform the format of the workshops and the patient group will be offered the opportunity of holding all of their meetings face-to-face, but the remaining groups will be conducted online. The postdoctoral researchers will manage the consensus workshops.

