## 9.2.2 Consensus workshops

We will set a priori criteria informed by the RAND/UCLA Appropriateness Method (46) for group consensus and undertake anonymised electronic voting, recording if and when agreement is reached. Data from the workshop will include anonymised rating scores for each round of voting and field notes and any design work produced during the workshop to inform our intervention development (including anonymised chat in video conferencing software). We will also audio-record the workshop to inform anonymised field notes. All workshop material will be anonymised, and any potentially identifying details will be removed from any design work produced during the workshop.

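### The workshop agreement rule as printed needs a median strictly above 7 although 7 lies in the agreeing region, so a panel unanimous at 7 is recorded as not agreeing

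*Protocol*

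**What the plan says.** Protocol section 6.4.2 sets up five stakeholder panels, "each containing 9 participants", which rate proposals on a 9-point scale over three rounds. It fixes the decision rule in advance and introduces it with "Consistent with the RAND/UCLA approach". For a nine-member panel, agreement is "a median of >7 on a 9-point Likert scale and no more than two members rating outside the 3-point region containing the median". The rule has two conditions:

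- **Level:** the panel median must be strictly above 7.
- **Dispersion:** at most two ratings may fall outside the region, which a parenthesis spells out as "i.e., 7–9 on a 9-point Likert scale".

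Section 9.2.2 refers again to criteria set beforehand and to "recording if and when agreement is reached". It gives no threshold of its own, so section 6.4.2 is the only place where the boundary is stated.

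**The concern.** The two conditions treat a rating of 7 differently. For dispersion, a member who votes 7 is inside the agreeing region and is not counted as dissenting. For level, a median of 7 is not enough. The region is described as the one that contains the median, and a median of 7 lies in 7 to 9, yet such a panel can never be recorded as agreeing, however closely its members concur.

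What is at stake is the consensus record from Stage 2. Section 6.4.2 gives the protocol's only numerical criterion for consensus. Followed literally, it classes some proposals that every panel member placed in the agreeing region as lacking consensus, and classes others with two members at the bottom of the scale as agreed. Because the criterion is meant to be fixed beforehand, moving the boundary after votes have been seen would look like selection.

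**Working it through.** The protocol gives no count or probability for this rule, so there is no figure to reproduce. The check applies the rule as printed.

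**Inputs (all from section 6.4.2).** Nine members per panel; ratings 1 to 9, taken as whole numbers; agreeing region 7, 8, 9; at most two ratings outside it; median strictly above 7.

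**Step 1: meaning of the median condition.** With nine ratings the median is the fifth in order, a whole number. A median above 7 therefore means 8 or 9, that is, at least five ratings of 8 or 9.

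**Step 2: three example panels.**

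| Ratings | Median | Outside 7–9 | Mean | Median > 7 (as printed) | Median ≥ 7 |
|---|---|---|---|---|---|
| nine 7s | 7 | 0 | 7.00 | not agreement | agreement |
| five 7s, four 9s | 7 | 0 | (35 + 36)/9 = 7.89 | not agreement | agreement |
| five 8s, two 7s, two 1s | 8 | 2 | (40 + 14 + 2)/9 = 6.22 | agreement | agreement |

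**Step 3: how many rating sets are affected.** Count unordered sets of nine ratings with k in 7 to 9 and 9 − k in 1 to 6. The sets meeting the dispersion condition number C(k+2, 2) × C(14−k, 5), for k = 7, 8, 9. Those that also have at least five ratings of 8 or 9 are found by summing (j + 1) over j = 5 to k, where j is the number of 8s and 9s, and multiplying by the same second factor.

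| k in 7–9 | Meet dispersion condition | Also median > 7 | Fail only on the median |
|---|---|---|---|
| 9 | 55 × 1 = 55 | 40 × 1 = 40 | 15 |
| 8 | 45 × 6 = 270 | 30 × 6 = 180 | 90 |
| 7 | 36 × 21 = 756 | 21 × 21 = 441 | 315 |
| Total | 1,081 | 661 | 420 |

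So 420 of 1,081 sets (38.9%) satisfy the dispersion condition, have a median of exactly 7, and fail only because the inequality is strict. In 15 of them all nine members are inside the region. Full enumeration of all rating sets gives the same totals.

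**Step 4: the rule with 7 included.** If the median need only be 7 or more, all 1,081 sets qualify. Any panel with at least seven of nine ratings in 7 to 9 already has a median of at least 7, so for this region the dispersion limit alone then decides.

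**The case against.** Three points on the other side carry weight.

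**The symbol may not be what the authors wrote.** A greater-than-or-equal sign can lose its lower bar in typing or in conversion from PDF. The parenthesis giving 7 to 9 would fit such a sign. If the source file shows it, the point falls. This stands as a reason to check the file first.

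**A stricter cut is logically possible.** One condition could test strength (median 8 or 9) and the other dispersion (judged on 7 to 9). Step 4 lends this some support: with 7 included, the median condition adds nothing for the agreeing region. So the two conditions are not formally incompatible. But the protocol neither states nor justifies a stricter cut, and the median also serves to locate the region, so its redundancy does not show that the strict sign was meant.

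**The consequence is limited.** A reader might infer that a proposal failing the rule is removed from Stages 3 to 5. The protocol does not say so. The plain English summary describes voting to decide which proposals matter most. In section 6.5 the research team works from Stage 1 and 2 data with the behaviour change wheel and the APEASE criteria. Section 9.2.2 keeps the ratings from each round along with field notes, so proposals with a median of 7 stay visible. A reader might also work out the chance that at least one of the five panels fails a well-supported proposal. That would need invented rating probabilities and independent raters, although one round is a moderated group rating. The protocol also states no rule that all five panels must agree.

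Nor can it be said here that the rule departs from the cited method, since the manual is not part of the documents. The protocol only claims consistency with it.

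**Conclusion.** As printed, the agreement rule is badly fixed at its boundary: 7 counts as agreeing for individual members but not for the panel median. The misclassification is certain for any panel with a median of exactly 7 and no more than two ratings outside the region, which covers 420 of the 1,081 rating sets that meet the dispersion limit. That is a count of possible patterns and says nothing about how often they will occur.

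The conclusion assumes that the strict sign is genuine, that ratings are whole numbers and that all nine members vote. It needs no outside source. It concerns what is recorded as consensus in Stage 2; the documents do not support going further and saying that proposals are lost from the pathway.

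**What to change.** 1. Check the symbol in the source file of section 6.4.2. If it already reads 7 or more, no change is needed beyond making sure that it displays correctly.
2. If it is a strict inequality, replace it with a median of 7 or more (≥ 7) and keep the limit of no more than two ratings outside 7 to 9.
3. If a stricter cut is intended, state before voting that a median of exactly 7 is not agreement, and why. Narrowing the region to 8 to 9 is not a substitute, because that has two points and the rule is built on a 3-point region.
4. If votes are already stored, tabulate them under both boundaries and disclose that this was done.

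Section 9.2.2 needs no edit because it states no threshold. The cost is one symbol or one sentence in a protocol correction; if votes exist, it is a re-tabulation of ratings that section 9.2.2 already has the team keep.

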#### 6.5 Stage 3: Decision-making

Based on data generated by WP2 Stages 1 and 2, the research team will use the behaviour change wheel to identify intervention functions and behaviour change techniques that will be most likely to achieve the change required (47). We will evaluate the interventions according to acceptability, practicability, effectiveness/cost-effectiveness, affordability, and safety/side-effects (APEASE) defined in the Behaviour Change Wheel (47).

